7.8.5 Others

7.8.5.1 Physical examination

Physical examination findings will be reported as relevant medical history/baseline condition (if a condition already exists before first administration of study treatment) or as AE (if condition emerges after first administration of study treatment) and will be summarized as such. No separate listing or analysis of physical examination findings will be prepared.

7.8.5.2 Standardized neurological assessment

Clinically relevant findings of the mental and neurological examination will be reported as adverse events (during the trial) or as baseline conditions (at screening). No separate listing or analysis of neurological examination findings will be prepared.

7.8.5.3 Suicidality assessment (C-SSRS)

Suicidality monitoring will be performed as described in Section 5.2.6 of the CTP, results will be listed. Additionally, frequency of subjects categorized by any question answered with

‘Yes’ (or all answered with ‘No’ or missing) will be presented. Results for subjects who answered any question with ‘Yes’ will additionally be listed. Findings will also be reported as AEs.

7.8.5.4 Assessment of dissociative symptoms (CADSS)

Frequency of subjects categorized by CADSS total score ‘0’ or ‘>=1’ will be presented by treatment (or treatment sequence) and time point. In addition, subjects with a total score >0 will be listed.

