### 1.2.6 Clinical experience in humans

To date, no clinical studies with BI 1569912 have been performed.

[figure not shown]
However, clinical information on compounds of the same (NR2B NAM) or related (unselective NMDA inhibitors) pharmacological classes are available.

[figure not shown]
In a phase II study with traxoprodil administered intravenously, transient dissociative symptoms such as out-of-body experience, tunnel vision, derealisation, or depersonalization were reported. They were dose dependent, transient in nature and resolved completely within hours. Other side effects were mild and included abnormal feeling, dizziness, paraesthesia, somnolence, dry mouth, abnormal urine odour, and an increase in blood pressure [\[R17-3810\]](#). The clinical development of traxoprodil was discontinued, probably for a CYP 2D6 liability or effects on the QT/QTc interval [\[P06-11048\]](#), [\[R19-1029\]](#).

[figure not shown]
In phase 2 studies with rislenemdaz, dizziness, headache, diarrhoea, dry mouth, somnolence, paraesthesia, and blood pressure increase were reported. Rislenemdaz did not lead to dissociative symptoms [\[R19-0986\]](#).

Overall, for these NR2B-specific negative allosteric modulators, no serious safety concerns have been identified.

For unspecific NMDA inhibitors, like esketamine, the most important side effects were transient CNS effects, like dissociation (altered time and sensory perception) and sedation as well as increases in blood pressure. In phase 3 studies with esketamine, transient dizziness, dissociative/ perceptual symptoms, nausea, vertigo, headache, dysgeusia, paraesthesia, hypaesthesia, sedation, and vomiting were reported. Dissociative and sedative side effects typically peaked within 2 h after drug administration and resolved within 6 h. Transient increases in blood pressure were also common.

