5.3 FURTHER ENDPOINTS

5.3.1 Safety parameters

Safety and tolerability of BI 1569912 will be assessed based on further safety parameters defined in **Section 2.2.2.1 of the CTP**:

- *AEs (including clinically relevant findings from the physical examination)*
- *Safety laboratory tests*
- *12-lead ECG*
- *Continuous ECG monitoring (SRD-Part, only)*
- *Vital signs (blood pressure, pulse rate, respiratory rate, body temperature)*
- *Columbia-Suicide Severity Rating Scale (C-SSRS)*
- *Standardized physical/ neurological assessment [only as part of AE analysis]*
- *Assessment of dissociative symptoms ([...] CADSS)*
- *Electroencephalogram (EEG) [i.e., safety EEG, abnormal or normal]*

CADSS

CTP: *The CADSS is a clinician administered measure of perceptual, behavioural and attentional alterations during active dissociative experiences. The scale contains 23 subjective items, each rated from 0 (not at all) to 4 (extremely).*

The total score of the CADSS is the sum of the 23 item scores, ranging from 0 to 92. Statistical analysis of the CADSS will be based on the total score.

12-lead ECG endpoints

For the definition of baseline and a summary of time points please refer to [Section 6.7](#).

Quantitative ECG endpoints:

The following quantitative ECG endpoints will be determined for the ECG variables QTcF, QT, HR, PR, QRS, RR and QTcB derived as described in [Section 10.1](#):

- absolute values (per time point)
- changes from baseline (per time point)
- percent changes from baseline (per time point; for HR, PR, QRS)

Categorical ECG endpoints

[figure not shown]
The following categorical ECG endpoints will be determined based on the quantitative ECG endpoints.

[figure not shown]
- New onset (meaning that this or a higher category was not present at baseline) of maximum QTcF interval > 450 to 480 msec, > 480 to 500 msec, or > 500 msec on treatment. For assignment of a particular subject to one of the above categories, all time points on-treatment (refer to [Table 6.7: 4](#) and [Table 6.7: 5](#)) will be considered.
- Maximum change from baseline in QT interval of ≤ 60 msec, or > 60 msec on treatment
- Maximum change from baseline in QTcF interval of ≤ 30 msec, > 30 to ≤ 60 msec, or > 60 msec on treatment

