7. PLANNED ANALYSIS

The format of the listings and tables will follow the BI guideline "Reporting of clinical trials and project summaries" ([6](#)).

The individual values of all subjects will be listed. Listings will be sorted by treatment or sequence group, subject number and visit (if visit is applicable in the respective listing). AE listings will be sorted by assigned treatment (see [Section 7.8.1](#) below for details). The listings will be contained in Appendix 16.2 (SDL) of the CTR.

The following standard descriptive statistical parameters will be displayed in summary tables of continuous variables:

N	number of non-missing observations
Mean	arithmetic mean
SD	standard deviation
Min	minimum
Median	median
Max	maximum

For plasma concentrations as well as for all PK parameters the following descriptive statistics will additionally be calculated:

CV	arithmetic coefficient of variation
gMean	geometric mean
gCV	geometric coefficient of variation

For PK parameters the following descriptive statistics will additionally be calculated:

P10	10 th percentile
Q1	1 st quartile
Q3	3 rd quartile
P90	90 th percentile

The data format for descriptive statistics of plasma concentrations will be identical with the data format of the respective concentrations. The descriptive statistics of PK parameters will be calculated using the individual values with the number of decimal places as provided by the evaluation program. Then the individual values as well as the descriptive statistics will be reported with three significant digits in the CTR.

Tabulations of frequencies for categorical data will include all possible CRF categories and will display the number of observations in a category as well as the percentage (%) relative to the respective treatment group. Percentages will be rounded to one decimal place. The category missing will be displayed if and only if there actually are missing values. Percentages will be based on all subjects in the respective subject set whether they have non-missing values or not.

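### The planned CADSS table shows how many subjects at each dose had any dissociative score, but not how high the scores were or how they changed from baseline

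*SAP*

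**What the plan says.** SAP 5.3.1 describes the instrument: "The scale contains 23 subjective items, each rated from 0 (not at all) to 4 (extremely"). It then gives the derived variable, "The total score of the CADSS is the sum of the 23 item scores, ranging from 0 to 92", and the basis of analysis: "Statistical analysis of the CADSS will be based on the total score".

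SAP 7.8.5.4 sets out the analysis. It begins "Frequency of subjects categorized by CADSS total score", with two categories, 0 and 1 or more, and these frequencies "will be presented by treatment (or treatment sequence) and time point". It adds: "In addition, subjects with a total score >0 will be listed". No mean, median, maximum, change from baseline or graded category is planned.

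Other parts of the documents bear on the point:

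- **Protocol 7.3.4** plans frequency tables for categorical safety data and tabulated descriptive statistics for continuous data. The protocol's safety endpoints include the assessment of dissociative symptoms (protocol 2.2.2.2).
- **SAP section 4** lists two changes to the planned analysis, neither about the CADSS, and says that everything else follows the protocol's statistical methods.
- **SAP 6.1** names the CADSS among the data analysed by treatment group in the SRD part and by treatment in the respective period in the BA/FE part, with baseline kept apart from post-baseline values.
- **SAP 6.7** defines baseline, except for PD endpoints and ECG variables, as the last off-treatment value before dosing.
- **SAP section 7** states: "The individual values of all subjects will be listed".
- **SRD flow chart, note on AEs**: dissociative symptoms are reported as AEs and are to be quantified with the CADSS. SAP 7.8.1 summarises AEs by maximum intensity.

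**The concern.** The SAP defines a graded score and then keeps only whether it is above zero. A subject with one item rated 1 counts the same as a subject with many items rated 4.

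Severity by dose is a natural question in a single rising dose study of this mechanism. Protocol 1.2.6 says of dissociative symptoms with another NR2B modulator, traxoprodil: "They were dose dependent, transient in nature and resolved completely within hours". Protocol 1.4.7 speaks of anticipated dissociative symptoms and plans quiet conditions to reduce them. A reader of the report will want to know whether the scores rose with dose, when they peaked and when they returned to the pre-dose level. The planned table answers these questions for the presence of any symptom only.

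The treatment of the CADSS also differs from that of the other numeric safety measures. Laboratory values (SAP 7.8.2), vital signs (7.8.3) and ECG intervals (7.8.4) all receive descriptive statistics and differences from baseline.

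**Working it through.** **1. The plan's own figure.** 23 items × 0 = 0 and 23 items × 4 = 92. The stated range is reproduced.

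**2. What the split keeps.** A 0 to 92 score has 93 possible values. The category of 1 or more holds 93 − 1 = 92 of them. If all 6 active subjects at one dose score 1, and all 6 at another dose score 92, both rows read 6/6. The table therefore carries no information on severity.

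**3. What the table still shows.** In the SRD part, treatment means each dose separately plus pooled placebo (SAP 6.1). With 7 dose groups in the SAP and 2 placebo subjects in each, pooled placebo has 7 × 2 = 14 subjects, against 6 per dose. Incidence by dose is visible. As an illustration only, 3/6 against 0/14 gives a two-sided Fisher p of 0.018, and 5/6 against 0/14 gives 0.0004.

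**4. Dose trend: incidence versus severity.** A simulation used pooled placebo and seven ordered dose groups, with a rank-correlation trend test at two-sided 5% and 3,000 runs. All incidences and mean scores are assumptions.

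| Assumed pattern across groups | Trend found, 0 versus ≥1 | Trend found, total score |
|---|---|---|
| Incidence rises 5% to 80%, severity constant | 99.5% | 99.3% |
| Incidence rises 5% to 80%, mean score among positives rises 2 to 30 | 99.3% | 99.7% |
| Incidence flat at 50%, mean score among positives rises 2 to 30 | 5.2% | 27.3% |

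Where incidence rises with dose, the split loses nothing here. Where only severity rises, it finds a trend at about the nominal error rate.

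**5. One dose against pooled placebo.** The assumptions are 6 versus 14 subjects, 83% of active subjects non-zero with mean 10 when non-zero, and placebo mean 1.5 when non-zero. Fisher's test on the split was compared with a Mann-Whitney test on the score. Ranges cover repeat simulations.

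| Assumed placebo subjects with score ≥1 | Split detects | Total score detects |
|---|---|---|
| 5% | 95–96% | 98–99% |
| 10% | 91–93% | 97–98% |
| 30% | 55–58% | 89% |
| 50% | 17–18% | 77–78% |

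The loss depends almost entirely on how often placebo subjects score above zero, and the documents do not give that rate. No such test is planned: the SRD part is descriptive (protocol 7.2). These figures illustrate lost information and are not properties of the trial.

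**6. Change from baseline.** Under SAP 6.7 the scheduled CADSS baseline is the assessment at 24 h before dosing. The flow chart has six post-dose assessments, at 1, 2, 4, 24, 48 and 72 h. A pre-dose frequency can appear in a table by time point. But a subject who scores 2 before and 2 after dosing counts the same after dosing as one who goes from 0 to 2, because no within-subject difference is summarised.

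**7. The BA/FE part.** 12 subjects over 6 sequences is 12 / 6 = 2 per sequence. A table by sequence would have two subjects per row and would show fed tablet, fasted tablet and solution only when decoded by period. SAP 6.1 already specifies treatment in the respective period, so SAP 7.8.5.4 is looser than the general rule it should follow.

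**The case against.** The strongest reply is that severity is not lost. All non-zero scores are listed, all individual values are listed, and dissociative symptoms enter the AE tables by maximum intensity. With 6 active subjects per dose, a listing shows the whole distribution. This stands, and it limits the point to the summary table. It does not remove it: a listing leaves the reader to build the comparison by dose, and AE intensity is a three-level judgement by an investigator who knows the treatment (protocol 4.1.5.1 and 5.2.7.1.5).

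It can also be said that a categorised total score is still an analysis of the total score, so SAP 5.3.1 and 7.8.5.4 do not strictly conflict. That is fair. The departure is from protocol 7.3.4's general plan for quantitative data.

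Some stronger readings are tempting, but the documents do not support them:

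- **That the table cannot show dose dependence.** It shows incidence by dose. Only dose dependence of severity is missing.
- **That no CADSS baseline is used.** SAP 6.7 supplies one and SAP 6.1 separates it from post-baseline values. Only the summary of change is missing.
- **That the BA/FE table will hide treatment.** SAP 6.1 sets analysis by treatment, and the mention of sequence is loose wording.
- **That dissociation is the key class effect.** Protocol 1.2.6 reports it with traxoprodil and reports none with rislenemdaz. It ranks it among the most important side effects only for unselective NMDA inhibitors.
- **That the stopping rules depend on this table.** Protocol 1.4.7 acts on severe drug-related AEs and does not use a CADSS score.

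**Conclusion.** The point holds as a free improvement of minor severity. The only CADSS summary shows incidence of any dissociative score by dose and time point. It shows neither severity, nor dose dependence of severity, nor within-subject change. Protocol 7.3.4 would lead a reader to expect descriptive statistics for a 0 to 92 score, and SAP section 4 does not record the difference.

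This conclusion rests on the text and on the range of the score, and needs no assumption about effect size. How much the split would hide in practice cannot be fixed from the documents. It is small if placebo subjects rarely score above zero or if incidence rises with dose. It is large if many placebo subjects have trivial scores or if only severity rises.

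**What to change.** In SAP 7.8.5.4:

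1. Add N, mean, SD, median, minimum and maximum of the total score, and of its change from the SAP 6.7 baseline, by treatment actually received and time point.
2. Add each subject's maximum post-dose score, summarised by dose and pooled placebo.
3. Delete the alternative of presenting results by treatment sequence, so that the section agrees with SAP 6.1.
4. Keep the 0 versus 1 or more table and the listing.

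The cost is a few lines of SAP text and the programming of the added summaries from scores already collected. No change to the protocol, the visits or the sample size is needed.

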7.8.5.5 Assessment of safety electroencephalogram (EEG)

Abnormal findings will be reported as baseline conditions (at screening) or AEs (during the trial), if judged clinically relevant by the investigator.

Frequency of subjects categorized by EEG abnormalities will be presented by treatment and day.

7.8.5.6 Body weight

[figure not shown]
Body weight will be analyzed descriptively, by visit.

[figure not shown]
8. TIMEPOINT OF RELEASE OF TREATMENT INFORMATION

[figure not shown]
The treatment information will be loaded into the trial database at trial initiation, i.e., the database will be handled open-label in accordance with the CTP.

[figure not shown]

11. HISTORY TABLE

Table 11: 1 History table

Version	Date (DD-MMM-YY)	Author	Sections changed	Brief description of change
Final	05-DEC-21		None	This is the final TSAP
